5.2.2.6 Management of Hypertension

Hypertension is a recognized side effect of treatment with drugs inhibiting VEGF signaling. Investigators should therefore ensure that participants enrolled to receive treatment with lenvatinib have BP of $\leq 150/90$ mm Hg at the time of study entry and, if known to be hypertensive, have been on a stable dose of antihypertensive therapy for at least 1 week before Cycle 1 Day 1. Early detection and effective management of hypertension are important to minimize the need for lenvatinib dose interruptions and reductions.

Regular assessment of BP should be as detailed in the Study Flow Chart (Section 6.1). Hypertension will be graded using NCI CTCAE v5.0, based on BP measurements only (and not on the number of antihypertensive medications). If the participant's initial BP measurement is elevated (ie, systolic BP ≥ 140 mm Hg or diastolic BP ≥ 90 mm Hg), the BP measurement should be repeated at least 5 minutes later.

One BP assessment is defined as the mean value of 2 measurements at least 5 minutes apart. If the BP assessment (ie, the mean of the 2 BP measurements obtained at least 5 minutes apart) is elevated (systolic BP ≥ 140 mm Hg or diastolic BP ≥ 90 mm Hg), a confirmatory assessment should be obtained at least 30 minutes later by performing 2 measurements (at least 5 minutes apart) to yield a mean value.

Antihypertensive agents should be started as soon as elevated BP (systolic BP ≥ 140 mm Hg or diastolic BP ≥ 90 mm Hg) is confirmed on 2 assessments at least 30 minutes apart. The choice of antihypertensive treatment should be individualized to the participant's clinical circumstances and follow standard medical practice. For previously normotensive participants, appropriate antihypertensive therapy should be started when systolic BP ≥ 140 mm Hg or diastolic BP ≥ 90 mm Hg is first observed on 2 assessments at least 30 minutes apart. For those participants already on antihypertensive medication, treatment modification may be necessary if hypertension persists.

Lenvatinib should be withheld in any instance where a participant is at imminent risk to develop a hypertensive crisis or has significant risk factors for severe complications of uncontrolled hypertension (eg, BP $\geq 160/100$ mm Hg, significant risk factors for cardiac disease, intracerebral hemorrhage, or other significant co-morbidities). Once the participant has been on the same antihypertensive medications for at least 48 hours and the BP is controlled, lenvatinib should be resumed as described below.

Participants who have had systolic BP ≥ 160 mm Hg or diastolic BP ≥ 100 mm Hg must have their BP monitored on Day 15 (or more frequently as clinically indicated) until systolic BP has been ≤ 150 mm Hg and diastolic BP has been ≤ 95 mm Hg for 2 consecutive treatment cycles. If a repeat event of systolic BP ≥ 160 mm Hg or diastolic BP ≥ 100 mm Hg occurs, the participant must resume the Day 15 evaluation until systolic BP has been ≤ 150 mm Hg and diastolic BP has been ≤ 95 mm Hg.

Hg for 2 consecutive treatment cycles. Participants will have the option of having BP measurements between visits obtained locally by a health care professional. A diary will be provided as a tool to aid the participant in collecting blood pressure evaluations between study visits.

The following guidelines should be followed for the management of systolic BP ≥ 160 mm Hg or diastolic BP ≥ 100 mm Hg confirmed on 2 BP assessments at least 30 minutes apart:

- Continue study drug and institute antihypertensive therapy for participants not already receiving antihypertensive therapy. Note: Eligibility of a participant that is receiving ≥ 3 antihypertensive medications prior to study entry will require PI approval.
- For those participants already on antihypertensive medication, the dose of the current agent may be increased, if appropriate, or 1 or more agents of a different class of antihypertensive should be added. Study treatment can be continued without dose modification.
- If systolic BP ≥ 160 mm Hg or diastolic BP ≥ 100 mm Hg persists despite maximal antihypertensive therapy, then lenvatinib administration should be interrupted and restarted at 1 dose level reduction only when systolic BP ≤ 150 mm Hg and diastolic BP ≤ 95 mm Hg and the participant has been on a stable dose of antihypertensive medication for at least 48 hours.
 - If systolic BP ≥ 160 mm Hg or diastolic BP ≥ 100 mm Hg recurs on the first dose reduction despite optimal management of hypertension with antihypertensive medications (either by dose increase or the addition of a different class of antihypertensive), then lenvatinib administration should be interrupted and restarted at an additional dose reduction only when systolic BP ≤ 150 mm Hg and diastolic BP ≤ 95 mm Hg and the participant has been on a stable dose of antihypertensive medication for at least 48 hours.
 - If systolic BP ≥ 160 mm Hg or diastolic BP ≥ 100 mm Hg recurs on the second dose reduction despite optimal management of hypertension with antihypertensive medications (either by dose increase or the addition of a different class of antihypertensive), then lenvatinib administration should be interrupted and restarted at a third dose reduction only when systolic BP ≤ 150 mm Hg and diastolic BP ≤ 95 mm Hg and the participant has been on a stable dose of antihypertensive medication for at least 48 hours.
 - Additional dose reduction should be discussed with the study PI.
- The following guidelines should be followed for the management of Grade 4 hypertension (life-threatening consequences):
 - Institute appropriate medical management

- Discontinue study drug

5.2.2.7 Management of Proteinuria

Regular assessment of proteinuria should be conducted as detailed in the Study Flow Chart (Section 6.0). Guidelines for assessment and management of proteinuria are as follows:

Detection and Confirmation

- Perform urine dipstick testing per the Study Flow Chart (Section 6.0)
- A 24-hour urine collection initiated as soon as possible and at least within 72 hours (or an immediate spot urine protein-to-creatinine ratio [UPCR] test) is required in the following situations:
 - The first (initial) occurrence of $\geq 2+$ proteinuria on urine dipstick while on study drug
 - A subsequent increase in severity of urine dipstick proteinuria occurring on the same lenvatinib dose level
 - When there has been a lenvatinib dose reduction and at the new dose level the urine protein dipstick result is $\geq 2+$.
 - A 24-hour urine collection (initiated as soon as possible and at least within 72 hours) to verify the grade of proteinuria is required when UPCR is ≥ 2.4 .

Grading of Proteinuria:

- Grading according to NCI CTCAE v5.0 will be based on the 24-hour urinary protein result if one has been obtained.

Management of lenvatinib administration will be based on the grade of proteinuria according to Table 5:

- In the event of nephrotic syndrome, lenvatinib must be discontinued.

Monitoring:

- Urine dipstick testing for participants with proteinuria $\geq 2+$ should be performed on D15 (or more frequently as clinically indicated) until the results have been 1+ or negative for 2 consecutive treatment cycles.

5.2.2.8 Management of Diarrhea

An anti-diarrheal agent should be recommended to the participant at the start of study treatment and participants should be instructed and educated to initiate anti-diarrheal treatment at the first onset of soft bowel movements. The choice of anti-diarrheal agent should be individualized to the participant's clinical circumstances and follow standard medical practice. If signs/symptoms of diarrhea persist despite optimal medical management, instructions contained in Table 5 should be

followed. If diarrhea does not improve, pembrolizumab-induced diarrhea should be considered and managed with corticosteroids as detailed in Table 3.

5.2.2.9 Management of Hepatotoxicity

Liver function tests (alanine transaminase [ALT], aspartate transaminase [AST], bilirubin levels) should be conducted as detailed in the Study Flow Chart (Section 6.1) and as clinically indicated. If signs/symptoms indicating liver injury occur, instructions contained in Table 5 should be followed. Appropriate supportive care should be provided together with close monitoring. If hepatic failure occurs, the study drug must be discontinued. It might not be possible to determine whether LFT abnormalities are due to pembrolizumab or lenvatinib. Therefore, both drugs should be held and if no improvement is seen, corticosteroids should be initiated.

5.2.2.10 Management of Thromboembolic Events

Participants should be advised to pay attention to symptoms suggestive of venous thromboembolic events which include acute onset of shortness of breath, dyspnea, chest pain, cough, hemoptysis, tachypnea, tachycardia, cyanosis, and deep vein thrombosis signs including lower-extremity swelling and warmth to touch or tenderness. In case any of these symptoms appear, participants should be instructed to report such symptoms promptly to the treating physician. If a thromboembolic event is confirmed, instructions contained in Table 5 should be followed. Appropriate supportive care should be provided together with close monitoring. If a participant experiences life-threatening (Grade 4) thromboembolic reactions, including pulmonary embolism, the study drug must be discontinued. Arterial thromboembolic events (eg, new onset, worsening, or unstable angina, myocardial infarction, transient ischemic attack, and cerebrovascular accident) of any grade require study treatment discontinuation.

5.2.2.11 Management of Posterior Reversible Encephalopathy Syndrome/Reversible

Encephalopathy Syndrome/ Reversible Posterior Leukoencephalopathy Syndrome

PRES/RPLS is a neurological disorder that can present with headache, seizure, lethargy, confusion, altered mental function, blindness, and other visual or neurological disturbances. Mild to severe hypertension may be present. MRI is necessary to confirm the diagnosis of PRES/RPLS. Appropriate measures should be taken to control BP. In participants with signs or symptoms of PRES/RPLS, instructions in Table 5 should be followed.

5.2.2.12 Management of Hypocalcemia

Serum calcium should be monitored per the Study Flow Chart (Section 6.1). Corrected serum calcium should be used to assess the grade of hypocalcemia per NCI CTCAE v5.0, using the following formula: $\text{Corrected calcium} = ([4 - \text{serum albumin in g/dL}] \times 0.8 + \text{serum calcium})$. The formula is not applicable when serum albumin concentration is normal (>4 g/dL); in such situations, the total (uncorrected) serum calcium should be used instead. Hypocalcemia should be

treated per institutional guidelines (e.g., using appropriate calcium, magnesium, and Vitamin D supplementation) until resolution.

5.2.2.13 Management of Hemorrhage

Instructions in Table 5 should be followed for the management of hemorrhage. Either resume at a reduced dose or discontinue lenvatinib depending on the severity and persistence of hemorrhage.

5.2.2.14 Dose Modifications for Overlapping Toxicities

For overlapping toxicities where it is unclear if the event is related to one or both drugs, it is recommended to hold both drugs, and initiate management per Dose Modification Guidelines for Lenvatinib-Related Adverse Events. If toxicity does not improve within 1 to 2 days or worsens, management per Dose Modification Guidelines for Pembrolizumab-Related Adverse Events should be followed.

Participants who experience an unacceptable toxicity that is attributed to lenvatinib in the opinion of the investigator and the PI, may permanently discontinue lenvatinib, but may continue with pembrolizumab, upon resolution of toxicity to Grade 0 or 1 or baseline, until unacceptable toxicity or progression. Participants who discontinue pembrolizumab due to untoward toxicities may not continue on the trial receiving only lenvatinib.

5.2.2.15 Other Allowed Dose Interruptions for Lenvatinib and Pembrolizumab

If a participant requires surgery during active treatment on the study, the stop time and restart time of lenvatinib should be as follows:

- For minor procedures: stop lenvatinib at least 3 days before the procedure and restart it at least 1 week after once there is evidence of adequate healing and no risk of bleeding. SRS is considered a minor procedure but does not require holding of lenvatinib.
- For major procedures: stop lenvatinib at least 1 week (5 half-lives) prior to surgery and then restart it at least 1 week after once there is evidence of adequate healing and no risk of bleeding.

Pembrolizumab may be interrupted for situations other than treatment-related AEs such as medical/surgical events or logistical reasons not related to study therapy. Participants should be placed back on study therapy within 3 weeks of the scheduled interruption, unless otherwise discussed with the Sponsor. The reason for interruption should be documented in the participant's study record.

Intervention After the End of the Study

There is no study-specified intervention following the end of the study.

5.2.3 Second Course *

All participants who stop study treatment with SD or better may be eligible for up to an additional 17 cycles (approximately 1 year) of pembrolizumab and lenvatinib treatment if they progress after stopping study treatment from the initial treatment phase. This retreatment is termed the Second Course Phase of this study and is only available if the study remains open and the participant meets the following conditions:

Either

- Stopped initial treatment with study treatment after attaining an investigator-determined confirmed CR based on RECIST 1.1, and
 - Was treated with at least 8 cycles of study treatment before discontinuing treatment, and
 - Received at least 2 cycles of pembrolizumab and lenvatinib beyond the date when the initial CR was declared

OR

- Had SD, PR, or CR and stopped study treatment after completion of 35 cycles (approximately 2 years) of study treatment for reasons other than disease progression or intolerability

AND

- Experienced an investigator-determined radiographic disease progression by RECIST 1.1 after stopping initial treatment, and
 - No new anticancer treatment was administered after the last dose of study treatment, and
 - The participant meets all of the safety parameters listed in the inclusion criteria and none of the safety parameters listed in the exclusion criteria, and
 - The study is ongoing

An objective response or disease progression that occurs during the Second Course Phase for a participant will not be counted as an event for the primary analysis of either endpoint in this study.

*Note: patients must have measurable disease at the start of protocol treatment to be eligible for this provision.

5.3 Treatment Allocation

This is a phase 2, non-randomized study with 2 cohorts of anti-PD-1/PD-L1 experienced patients with untreated brain metastases: 1) melanoma and 2) RCC. After establishing eligibility, patients will undergo fresh biopsy of a metastatic site, if feasible. The biopsy requirement can be waived

if there is not an easily accessible site to biopsy or if a biopsy is determined to be unfeasible by the treating physician after discussion with the study PI. Archived metastatic tumor tissue, including prior CNS tumor tissue, should also be submitted, if available. The tumor tissue will be studied retrospectively for PD-L1 expression, TIL characteristics, and other immune and angiogenic markers that may predict sensitivity to this drug combination. Pembrolizumab 200mg IV every 3 weeks will be administered in combination with lenvatinib 20 mg PO daily.

MRI of the brain will be obtained after 6 weeks of therapy for initial assessment of efficacy by mRECIST, and a confirmation scan will be performed at 12 weeks. CT body scans (and/or MRI or PET CT as clinically indicated) will also be done at these times to evaluate for extracranial response by RECIST. The next MRI brain or body imaging will be done every 12 weeks thereafter. Patients will continue on study until they have overall disease progression in either their clinically evaluable CNS lesions or in their systemic metastases, toxicities that preclude continuing the study drug, withdrawal from study, termination of study, or death. Dose reductions for immune-related toxicities will not be allowed.

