Archival tissue from extracranial and/or CNS metastases will be obtained, if available, for correlative studies. A baseline pre-treatment fresh biopsy will also be required from an accessible metastasis unless there is not an easily accessible site to biopsy or if a biopsy is determined to be unfeasible by the treating physician after discussion with the study PI. The tumor tissue will be studied retrospectively for PD-L1 expression, TIL characteristics, and other immune and angiogenic markers that may predict sensitivity to this drug combination.

First response assessment will be performed at 6 weeks and will include MRI of the brain and CT body scans (or other clinically indicated body imaging such as MRI or PET CT) to assess systemic disease. Brain metastasis response will be determined using modified RECIST (mRECIST) 1.1 criteria, and extracranial disease response will be determined using RECIST 1.1. Responses will be confirmed with repeat imaging done at 12 weeks. Subsequent imaging will be performed at 12-week intervals thereafter and include an MRI of the brain along with body imaging, which may include CT, MRI, or PET/CT, as clinically indicated. Patients will discontinue treatment for disease progression,

[figure not shown]
unacceptable toxicity, patient withdrawal from the study, termination of study, or death. Patients may be treated beyond progression of intracranial metastases after consultation with the study PI, provided symptomatic lesions are treated with stereotactic radiosurgery (SRS) or surgery. Dose reduction of pembrolizumab for immune-related toxicities is not permitted. Dose-reduction of lenvatinib for related toxicities is permitted.

Number of Patients:

A total of up to 62 eligible patients will be enrolled (27 patients with melanoma with allowance for 3 additional patients if any are unevaluable and 29 patients with RCC with allowance for 3 additional patients if any are unevaluable). Either cohort can be stopped for futility according to Simon's two-stage design. The study will accrue for approximately 36 months and will be open for approximately 24 additional months as patients on study are followed.

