5.5.4 Local Therapy and Treatment Beyond Disease Progression

Local therapy for brain metastases:

Local therapy in the form of craniotomy, LITT, or SRS can be performed on symptomatic brain lesions prior to assessment for study eligibility, provided all neurologic side effects from the procedure have resolved and all other eligibility criteria are met. At any time point throughout the study, local therapy (surgery, LITT, or SRS) will be administered to a lesion that becomes clinically concerning if deemed necessary by the investigators. This can be followed by continuation on pembrolizumab and lenvatinib, provided that the patient is otherwise benefiting from therapy and has stable disease or disease shrinkage in other lesions by RECIST criteria. Approval from the study PI or co-PIs is required to continue treating the patient on pembrolizumab and lenvatinib. Craniotomy and LITT are considered major procedures and require temporary holding of lenvatinib as detailed in Section 5.2.2.15. SRS is considered a minor procedure and does not require holding of lenvatinib. Further details for holding lenvatinib are detailed in Section 5.2.2.15.

A brain metastasis that has been treated locally will not be considered evaluable for response and will not be included when calculating the sum of largest dimensions. If the treated lesion constitutes >25% of the target lesions (for example, if one of three target lesions is treated locally), this will be considered progressive disease. If >75% of the baseline lesions are not treated with local therapy and evaluable by imaging, the patient will be considered evaluable, and response for the primary endpoint analysis will be assessed based on the remaining lesions. Additional response evaluation will be performed which will consider those patients who require local therapy while on study as having PD at the time of local therapy.

Local therapy for extra-cerebral metastases:

Local surgery or radiation therapy (if indicated for palliative measures only after discussion with the study PI or co-PIs) may be permitted and the patient can continue to receive pembrolizumab and lenvatinib provided there is otherwise evidence of clinical benefit from treatment (i.e. stable disease or response in measurable lesions). The criteria applied for assessing response is detailed in Section 7.1.2.9.

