5.6 Participant Withdrawal/Discontinuation Criteria

Discontinuation of study intervention does not represent withdrawal from the study.

As certain data on clinical events beyond study intervention discontinuation may be important to the study, they must be collected through the participant's last scheduled follow-up, even if the participant has discontinued study intervention. Therefore, all participants who discontinue study intervention prior to completion of the protocol-specified treatment period will still continue to participate in the study as specified in Section 7.1.4.

Participants may discontinue study intervention at any time for any reason or be discontinued from the study intervention at the discretion of the investigator should any untoward effect occur. In addition, a participant may be discontinued from study intervention by the investigator or the study PI if study intervention is inappropriate, the study plan is violated, or for administrative and/or other safety reasons. Specific details regarding procedures to be performed at study intervention discontinuation are provided in Section 7.1.5.3.

A participant must be discontinued from study treatment but continue to be monitored in the study for any of the following reasons:

- The participant or participant's legally acceptable representative requests to discontinue study treatment.
- Confirmed radiographic disease progression outlined in Section 7.1.2.9. Patients who are believed to be deriving benefit based on the discretion of the investigator and PI are allowed to continue.
- Any progression or recurrence of any malignancy, or any occurrence of secondary malignancy that requires active treatment. Exceptions to secondary malignancy include basal cell carcinoma of the skin, squamous cell carcinoma of the skin, new non-ulcerated primary melanoma <1 mm in depth with no nodal involvement, or carcinoma in situ (eg, breast carcinoma, cervical cancer in situ) that have undergone potentially curative therapy. Exceptions should be discussed with the study PI prior to continuing therapy or remaining in follow-up.
- Unacceptable adverse experiences as described in Section 5.2.2.

- The participant has a medical condition or personal circumstance which, in the opinion of the investigator and/or sponsor, placed the participant at unnecessary risk from continued administration of study treatment.
- The participant has a confirmed positive serum pregnancy test.

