- Noncompliance with study treatment or procedure requirements
- Recurrent Grade 2 pneumonitis, and other AEs that may require treatment discontinuation per Section 5.2.2 (Dose Modification).
- Discontinuation of treatment may be considered for participants who have attained a confirmed complete response (CR) and have been treated for at least 8 cycles (at least 24 weeks), receiving 2 cycles of the combination including 2 doses of pembrolizumab and at least 80% of the planned doses of lenvatinib beyond the date when the initial CR was declared. These participants may be eligible for second course treatment described in Section 5.2.3.
- The participant is lost to follow-up
- Completion of 35 treatment cycles (approximately 2 years) with pembrolizumab and lenvatinib. Note: Participants experiencing a clinical benefit may continue on lenvatinib alone beyond this time point until unacceptable toxicity or disease progression upon study PI consultation and approval (See Section 5.2.3 for additional details).

Note: The number of treatments is calculated starting with the first dose. Participants who stop the combination after receiving 2 years of treatment may be eligible for retreatment if they progress after stopping study treatment provided they meet the requirements detailed in Section 5.2.3. Participants may be retreated in the Second Course Phase (Retreatment) for up to an additional 17 cycles (approximately 1 year).
- Administrative reasons

A participant may be discontinued from study treatment but continue to be monitored in the study for any of the following reasons:

- Discontinuation of trial treatment with pembrolizumab and lenvatinib may be considered for participants who have attained a confirmed CR and have been treated for at least 24 weeks, receiving at least 2 doses of pembrolizumab beyond the date when the initial CR was declared.

Note: The number of treatments is calculated starting with the first dose of pembrolizumab.

- Progressive disease and/or lack of clinical benefit.

Note: Participants will be permitted to continue treatment beyond RECIST 1.1-defined progression provided investigator-assessed clinical stability is observed, and the participant is tolerating study drug (Section 5.5.4). Treatment beyond PD may be permitted upon study PI consultation and approval.

Participant Withdrawal From the Study

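### The sections on stopping or continuing treatment at progression differ in scope and test, so a clinically stable patient with extracranial progression and a controlled brain gets different answers

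*Combined protocol and SAP*

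**What the plan says.** Five places govern treatment at or after progression.

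- **Section 5.3 (Treatment Allocation):** "Patients will continue on study until they have overall disease progression in either their clinically evaluable CNS lesions or in their systemic metastases". Toxicity, withdrawal, study termination and death are the other end points listed. No exception follows.
- **Section 2.1 (Trial Design):** the default is "Patients will discontinue treatment for disease progression". One exception is given: "Patients may be treated beyond progression of intracranial metastases after consultation with the study PI", on condition that symptomatic lesions receive radiosurgery or surgery. Systemic progression has no exception.
- **Section 5.5.4 (Local Therapy and Treatment Beyond Disease Progression):** after local therapy to a brain lesion, both drugs may continue "provided that the patient is otherwise benefiting from therapy and has stable disease or disease shrinkage in other lesions by RECIST criteria", with approval from the PI or a co-PI. After local therapy to an extracerebral lesion, they may continue "provided there is otherwise evidence of clinical benefit from treatment (i.e. stable disease or response in measurable lesions").
- **Section 7.1.2.9.2 (Tumor Imaging During the Study):** patients with progression may continue at the discretion of the investigator and study PI if they meet the conditions of Section 5.5.4. This carries the lesion conditions beyond patients who had local therapy.
- **Section 5.6 (Withdrawal/Discontinuation):** the mandatory list includes "Confirmed radiographic disease progression outlined in Section 7.1.2.9", followed by an exception for patients whom the investigator and PI believe to be benefiting. The next mandatory item again names progression of any malignancy. The optional list then includes progressive disease, with the note "Participants will be permitted to continue treatment beyond RECIST 1.1-defined progression provided investigator-assessed clinical stability is observed". That note also requires that the drug be tolerated and that the PI approve, and it cites Section 5.5.4.

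**The concern.** A stopping rule for progression should give one answer for one patient. Here the permitted scope runs from none, to brain progression only, to any RECIST 1.1 progression. The test for continuing is in turn the state of other lesions on imaging, perceived benefit, or clinical stability with tolerability. These tests can give opposite results in the same patient.

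Four things are at stake:

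- **Exposure and adverse events.** Section 7.2 collects adverse events from allocation to a fixed time after treatment ends, so longer treatment means a longer collection window.
- **OS.** It is estimated from the start of study drug. Its interpretation depends on how many patients stayed on both drugs after progression.
- **Duration of intracranial response.** Section 8.3 treats a brain response as ongoing when the body has progressed. The patients to whom this convention applies are those for whom the stopping rule is unclear.
- **Follow-up after progression.** Section 7.1.2.9.2 continues imaging until progression is identified. Section 7.1.5.3.3 moves patients with confirmed progression to telephone contact for survival. The flow chart appears to mark imaging under survival follow-up as well. Continued brain imaging after body progression is therefore not clearly assured for a patient who stops.

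**Working it through.** No figure in the plan is at issue, so the check sets the sections side by side for three patients. All three are clinically stable and tolerating treatment, and in each the PI is willing to approve continuation.

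| Section | A: several body lesions progress, brain controlled | B: several asymptomatic brain lesions progress, body stable | C: one symptomatic brain lesion progresses and is treated locally, all others stable |
|---|---|---|---|
| 5.3 | Ends | Ends | Ends if the lesion counts as CNS progression |
| 2.1 | Stops; outside the only exception | May continue | May continue |
| 5.5.4 through 7.1.2.9.2 | Lesion condition not met | Lesion condition not met | May continue |
| 5.6, mandatory list | Stops on confirmed progression unless judged to be benefiting | Same | Same |
| 5.6, optional list and note | May continue | May continue | May continue |

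**Patient A** is the clear conflict. Sections 5.3 and 2.1 and the lesion condition of 5.5.4 all point to stopping. Both entries in 5.6 allow continuation, one on perceived benefit and the other on clinical stability.

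**Patient B** also gets mixed answers. Section 2.1 and the 5.6 note allow continuation; 5.3 and the lesion condition do not.

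**Patient C** gets the same permission from 2.1, 5.5.4 and 5.6. Only 5.3, read without exceptions, differs. So the conflict does not reach every progression.

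**Cross-reference.** The 5.6 note cites 5.5.4. If that imports the lesion condition, the citation defeats the note's own test for patient A, who is clinically stable but has progressing measurable lesions. If it does not, 5.6 and 7.1.2.9.2 set different tests for the same decision. Either way the text needs a decision.

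**Confirmation.** The mandatory item in 5.6 speaks of confirmed progression and points to Section 7.1.2.9. Within that section, repeat imaging to confirm progression is described for the second course (7.1.2.9.3) and in the PFS definition (7.1.2.9.8). The text on imaging during initial treatment (7.1.2.9.2) describes no such step. Sections 2.1 and 5.3 do not say whether confirmation is needed.

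**PFS.** Section 7.1.2.9.8 dates the event at the first documentation of progression that is later confirmed, in brain or body, or at death. That definition does not refer to whether treatment continued, so the event date does not depend on which stopping rule is followed.

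**The case against.** The best defence is that these sections form a default with exceptions. Section 2.1 states a default and then an exception. The mandatory item in 5.6 carries its own exception, so the two 5.6 entries largely agree in outcome: both let a patient continue with PI agreement. The flow chart asks for additional consent at initial RECIST 1.1 progression, which fits a planned continuation pathway. Section 5.3 is a summary, and it says on study rather than on treatment; Section 5.6 itself separates the two. The lesion conditions in 5.5.4 are written for patients who had local therapy.

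Much of this stands. The double listing in 5.6 is untidy more than contradictory, and 5.3 alone would be a weak basis, although it does list toxicities that preclude continuing study drug. On confirmation, 2.1 and 5.3 are less specific than 5.6 and do not contradict it.

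The defence fails on the exceptions themselves. They differ in scope (intracranial only against any RECIST 1.1 progression) and in test. Section 7.1.2.9.2 extends the 5.5.4 conditions to progression generally.

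A reader might also infer that continuation will vary from site to site. The documents do not show that. Every route for continuing after progression involves the study PI, through consultation, discretion or approval, and this central step limits variation between sites. What is missing is the criterion the PI should apply.

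**Conclusion.** The point holds as an inconsistency in operative text. It is clearest for extracranial progression in a clinically stable patient with a controlled brain, and also present for progression in several asymptomatic brain lesions. It affects exposure, adverse event counts, the interpretation of OS and the duration of intracranial response. It does not affect the PFS event date.

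Its size cannot be stated from the documents. A reader might apply the PFS medians quoted in the background (7.6 months in melanoma, 11.7 months in RCC) to the planned cohorts and call the resulting events affected. That does not follow. Those medians come from other study populations, and the count would include deaths, patients who are unstable or not tolerating treatment, and patients such as C above for whom 2.1, 5.5.4 and 5.6 agree.

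A reader might also infer a loss of power for the primary endpoint, because a week-6 brain response needs confirmation at 12 weeks and a patient stopped for body progression could miss that scan. This is possible, but the documents give no basis for the fraction of responders who would be lost, so no loss is claimed.

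The conclusion rests on reading 5.3 as governing treatment as well as participation, and on taking the 7.1.2.9.2 cross-reference at face value. Without the first of these, 2.1 and 5.6 still disagree on extracranial progression.

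**What to change.** Reconcile Sections 2.1, 5.3, 5.5.4, 5.6 and 7.1.2.9.2 into one rule placed in 5.6, and have the other sections refer to it. The rule should state:

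- how it applies to brain-only, body-only and combined progression;
- which test governs continuation, and whose approval is needed;
- whether progression must be confirmed and, if so, where that confirmation is defined for the initial treatment period.

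List progression once in 5.6, and make the neighbouring item on progression of any malignancy consistent with it. The content of the rule is a clinical decision for the sponsor; none is proposed here.

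In Section 8.3, add that the number of patients treated beyond progression will be reported by cohort alongside OS and adverse events. It can be derived from dosing and progression dates.

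The cost is amendment wording and its IRB review. No visits, scans or new data fields are needed for this.
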